10.8 Appendix 8: Rapid alert procedures

Not applicable.

This document cannot be used to support any marketing authorization application and any extensions or variations thereof.
PUBLIC COPY

10.9 Appendix 9: Country-specific requirements

The country-specific requirements for Japan will be provided separately.

This document cannot be used to support any marketing authorization application and any extensions or variations thereof.

PUBLIC COPY

10.10 Appendix 10: Abbreviations and trademarks

AE	adverse event
ALP	alkaline phosphatase
ALT	alanine aminotransferase
AST	aspartate aminotransferase
BRV	brivaracetam
CI	confidence interval
CRO	contract research organization
CYP	cytochrome P450
COVID-19	coronavirus disease 2019
CV	coefficient of variation
DBP	diastolic blood pressure
DMC	Data Monitoring Committee
ECG	electrocardiogram
eCRF	electronic Case Report Form
GCP	Good Clinical Practice
GMR	geometric mean ratio
IB	Investigator's Brochure
ICF	informed consent form
ICH	International Council for Harmonisation
IMP	investigational medicinal product
IRB	Institutional Review Board
iv	intravenous
MedDRA®	Medical Dictionary for Regulatory Activities
PDILI	potential drug-induced liver injury
PED	Pharmaceutical Evaluation Division
PK	pharmacokinetics
PKS	Pharmacokinetic Set
POS	partial-onset seizures
PSEHB	Pharmaceutical Safety and Environmental Health Bureau
QTcF	QT interval corrected for heart rate with Fridericia's formula
SAE	serious adverse event

SARS-CoV-2	severe acute respiratory syndrome coronavirus 2
SAP	Statistical Analysis Plan
SBP	systolic blood pressure
SD	standard deviation
SFU	Safety Follow-Up
SS	Safety Set
SV2A	synaptic vesicle protein 2A
TEAE	treatment-emergent adverse event
ULN	upper limit of normal

This document cannot be used to support any marketing application and any extensions or variations thereof.
PUBLIC COPY

10.11 Appendix 11: Protocol amendment history

The Protocol Amendment Summary of Changes Table for the current amendment is located before the Table of Contents.

Amendment 1 (14 Dec 2023)

This document cannot be used to support any marketing authorization application and any extensions or variations thereof.

PUBLIC COPY

## VERSION HISTORY

SAP Version	Date	Change	Rationale
Final	19 Mar 2024	Not Applicable	Original version
Amendment 0.1	Date of Last Signature	Update the analysis set for PK parameter listing in section 4.6.1.1.2	To make consistence with TLF mock shell
Amendment 1	28 Jun 2024	Update the PK parameters that to be summarized in section 4.6.1.1.2; Remove percent deviation from section 4.6.1.1.1.	To make consistence with TLF mock shell; DEM decision due to meaninglessness of percent deviation.

This document cannot be used to support any marketing authorization application and any extensions or variations thereof.  
PUBLIC COPY

## 1 INTRODUCTION

The purpose of this Statistical Analysis Plan (SAP) is to provide all information that is necessary to perform the required statistical analysis of study EP0231. This SAP should be read in conjunction with the study protocol amendment 1.0 that provides all necessary background information and rationale for the current study and its design.

The SAP is based on the following study documents:

- Protocol Amendment 1.0: 14 Dec 2023
- Electronic Case Report Form (eCRF) v1.0: 21 Dec 2023

### 1.1 Objectives and endpoints

**Table 1-1: Objectives and Endpoints**

Objectives	Endpoints
Primary objective	
• To assess bioequivalence between the BRV 50mg tablet and BRV 50mg dry syrup after multiple oral doses in healthy male Japanese participants	Primary PK endpoints from plasma BRV concentrations: 

• <math>C_{max,ss}</math>

• <math>AUC_{tau}</math>

Secondary objective	
• To evaluate the safety and tolerability of multiple oral doses of the BRV 50mg tablet and BRV 50mg dry syrup in healthy male Japanese participants	Secondary safety endpoints: 

• Incidence of TEAEs

• Incidence of treatment-emergent SAEs

• Incidence of TEAEs leading to discontinuation

Other objectives	
• To evaluate other PK parameters after multiple oral doses of the BRV 50mg tablet and BRV 50mg dry syrup in healthy male Japanese participants	Other PK endpoints from plasma BRV concentrations: 

• <math>C_{trough}</math>

• <math>CL_{ss}/F</math>

• <math>t_{max,ss}</math>

• To further evaluate the safety and tolerability after multiple oral doses of the BRV 50mg tablet and BRV 50mg dry syrup in healthy male Japanese participants	Other safety endpoints: 

• Change from Baseline in clinical laboratory test parameters (ie, hematology, clinical chemistry, and urinalysis)

• Change from Baseline in vital signs (SBP, DBP, body temperature, respiratory rate, and heart rate)

• 12-lead ECG parameters and findings

• Physical examinations

AUCtau=area under the curve during a dosing interval at steady state; BRV=brivaracetam; CLss/F=apparent total body clearance at steady state; Cmax,ss=maximum plasma concentration at steady state; Ctrough=measured concentration at the end of a dosing interval at steady state; DBP=diastolic blood pressure; ECG=electrocardiogram; PK=pharmacokinetics; SAE=serious adverse event; SBP=systolic blood pressure; TEAE=treatment-emergent adverse event; tmax,ss=time of Cmax,ss

## 1.2 Study design

EP0231 is a single-center, multiple-dose, open-label, randomized, group sequential design, 2-way cross-over study to assess the bioequivalence of BRV 50mg tablet and BRV 50mg dry syrup in healthy male Japanese participants after oral administration under fasted conditions. In addition, the safety and tolerability of BRV will be evaluated.

[figure not shown]
Participants will enter a Screening Period (2 to 28 days before administration of investigational medicinal product [IMP]), and eligible participants will start the Dosing Period. The Dosing Period consists of 2 periods (Dosing Period 1 and Dosing Period 2) of 5 days each (Day -1 to Day 4) with a total of 5 administrations of BRV 50mg on Day 1 and Day 2 (morning and evening doses 12 hours apart), and Day 3 (morning dose only).

Participants will receive 1 of the following treatments in each Dosing Period under fasting conditions according to randomly assigned treatment sequences (A-B or B-A):

- Treatment A – multiple doses of BRV 50mg tablets
- Treatment B – multiple doses of BRV 50mg dry syrup (1.25g of granules for oral suspension 4% w/w)

The Dosing Periods will be separated by a Wash-Out Period (minimum of 6 days and preferably no more than 10 days between the final dose in Dosing Period 1 and the first dose in Dosing Period 2 for each participant) and followed by a Safety Follow-Up (SFU) Visit, 7 to 9 days after the last administration of IMP. Participants who prematurely discontinue the IMP/study will be encouraged to return for an SFU Visit, 7 to 9 days after the final IMP administration. Refer to the study schematic in [Figure 1-1](#).

**Figure 1-1: Schematic Diagram**

BRV=brivaracetam; DMC=Data Monitoring Committee; IMP=investigational medicinal product; max=maximum; min=minimum; SFU=Safety Follow-Up; w/w=weight/weight

a Following a Screening Period (up to 27 days before the start of Dosing Period 1), eligible participants will be randomly assigned to 1 of 2 treatment sequences (A-B or B-A) before dosing in Dosing Period 1, after all Day -1 assessments have been completed. After the first cohort (approximately 60 evaluable participants) has completed both Dosing Periods, an interim analysis will be performed, and an internal DMC will determine whether the primary objective is achieved, futility of the study is confirmed, or whether the study should continue with recruitment of the second cohort (approximately 30 evaluable participants).

b Each Dosing Period is 5 days each (Day -1 to Day 4). Brivaracetam 50mg will be administered twice daily (morning and evening doses 12 hours apart) as 50mg tablets (Treatment A [Reference]) or dry syrup (1.25g of BRV granules for oral suspension 4% w/w; Treatment B [Test]). On Day 1 and Day 2, participants will fast for at least 2 hours before and after IMP administration. On Day 3, only the morning dose will be administered, and the participants will fast for 10 hours before and 4 hours after IMP administration. For each Dosing Period, participants will be admitted to the study site on Day -1 (1 day before dosing) and will be discharged on the morning of Day 4, approximately 24 hours after last administration of IMP in each Dosing Period, at the discretion of the Investigator.

c The Dosing Periods will be separated by a Wash-Out Period (minimum of 6 days and preferably no more than 10 days between the final dose in Dosing Period 1 and the first dose in Dosing Period 2) for each participant.

d An SFU Visit will occur 7 to 9 days after the final IMP administration. Participants who prematurely discontinue the IMP/study will be encouraged to return for an SFU Visit within 7 to 9 days after the final IMP administration.

The Schedule of Activities is provided in [Table 1-2](#).

This document cannot be used to support any marketing authorization application and any extensions or variations thereof.

PUBLIC COPY

**Table 1-2: Schedule of Activities**

Procedure	Screening Period	Dosing Period 1 or Dosing Period 2 a					SFU b
	2 to 28 days before administration of IMP	Check in Day -1	Day 1	Day 2	Day 3	Day 4	
Written informed consent	X						
Demographics, habits, and lifestyle	X						
Verification of inclusion/exclusion criteria	X	X					
Verification of withdrawal criteria c		X	X	X	X	X	
Medical/surgical history	X	X					
Physical examination	X	X				X	X
Height and weight	X						
Viral serology (HBsAg, HCV, HIV, and syphilis)	X						
Alcohol and drug (including cotinine) testing	X	X					
COVID-19 precautions d	X	X					X
Vital signs e	X	X	X	X	X	X	X
Clinical laboratory tests (hematology, clinical chemistry, and urinalysis)	X	X				X	X
Randomization f		X					
12-lead ECG g	X		X			X	X
IMP administration h			X	X	X		
Blood sampling for PK i			X	X	X		
Recording of prior and concomitant medication and procedures	X	X	X	X	X	X	X
Recording of AEs	X	X	X	X	X	X	X
Confinement		X	X	X	X	X j	

AE=adverse event; BRV=brivaracetam; COVID-19=coronavirus disease 2019; ECG=electrocardiogram;  
HBsAg=hepatitis B surface antigen; HCV=hepatitis C virus; HIV=human immunodeficiency virus;  
IMP=investigational medicinal product; PK=pharmacokinetic(s); SFU=Safety Follow-Up; w/w=weight/weight

**Table 1-2: Schedule of Activities**

Procedure	Screening Period 2 to 28 days before administration of IMP	Dosing Period 1 or Dosing Period 2 a					SFU b 7 to 9 days after the last administration of IMP
		Check in Day -1	Day 1	Day 2	Day 3	Day 4	

a Each participant will enter 2 Dosing Periods, separated by a Wash-Out Period. Dosing Period 2 will begin after the Wash-Out Period (minimum of 6 days and preferably no more than 10 days between the final IMP administration in Dosing Period 1 and the first IMP administration in Dosing Period 2).

b An SFU Visit will occur 7 to 9 days after the last administration of IMP. Participants who prematurely discontinue the IMP/study will be encouraged to undergo an SFU Visit within 7 to 9 days after the last administration of IMP.

c Confirmation that participants do not fulfill the withdrawal or stopping criteria (Section 7 of the protocol) will occur on Day -1, before dosing on Days 1, 2, and 3, and prior to discharge on Day 4.

d Coronavirus disease 2019 precautions will be performed in alignment with the study site's local requirements (refer to Section 2.3.1 of the protocol for additional details).

e Vital signs (blood pressure [systolic blood pressure and diastolic blood pressure], heart rate, respiratory rate, and body temperature) will be taken at the Screening Visit; for each Dosing Period (on Day -1 check in, Day 1 predose and 12 hours postdose [before the evening dose is administered]), Day 2 [premorning dose] and Day 3 predose, and Day 4 prior to discharge); and at the SFU Visit.

f Randomization will occur only for Dosing Period 1; either on Day -1 after all assessments for Day -1 are performed or Day 1 before any assessments for Day 1 are performed. Each participant will be randomly assigned to 1 of 2 treatment sequences (A-B or B-A).

g Single 12-lead ECGs will be recorded at Screening, for each Dosing Period (Day 1 predose and Day 4 prior to discharge), and at the SFU Visit.

h Investigational medicinal product administration: Brivaracetam 50mg will be administered twice daily (approximately 12 hours apart) as 50mg tablets (Treatment A [Reference]) or dry syrup (1.25g of BRV granules for oral suspension 4% w/w; Treatment B [Test]). On Day 1 and Day 2, participants will fast for at least 2 hours before and after IMP administration. On Day 3, only the morning dose will be administered, and the participants will fast for 10 hours before and 4 hours after IMP administration.

i For each Dosing Period, blood samples for PK analysis will be collected on Day 1 (before the morning and evening doses [0 and 12hr]), Day 2 (before the morning and evening doses [24 and 36hr]), and Day 3 (predose [48hr] and 10min, 15min, 20min, 30min, 45min, 60min, 75min, 90min, 2hr, 6hr, 9hr, and 12hr postdose).

j Participants will check out of the clinical unit the morning of Day 4, approximately 24 hours after the final dose of IMP administered, at the discretion of the Investigator.

## 2 STATISTICAL HYPOTHESES

The study is aimed to demonstrate the bioequivalence between BRV 50mg dry syrup (1.25g of granules for oral solution 4% w/w, corresponding to 50mg of BRV) (Test) and BRV 50mg tablet (Reference) after multiple oral doses according to  $C_{max,ss}$  and  $AUC_{tau}$ .

Null hypothesis ( $H_0$ ): the adjusted Test/Reference geometric mean ratio is smaller than 0.80 or larger than 1.25.

Alternative hypothesis ( $H_1$ ): the adjusted Test/Reference geometric mean ratio is within 0.80 to 1.25.

The confidence intervals (CIs) of the adjusted Test/Reference geometric mean ratio will be calculated corresponding to the Lan-DeMets alpha spending function approximating a Pocock boundary ([Lan and DeMets, 1983](#)), while maintaining the overall 2-sided significance level of 0.1.

Based on the hypotheses, bioequivalence between the Test (dry syrup) and Reference (tablet) formulations will be concluded if the CIs for  $C_{max,ss}$  and  $AUC_{tau}$  are contained in the range of 0.80 to 1.25.

In the case that the CIs for  $C_{max,ss}$  and  $AUC_{tau}$  are not contained in the range of 0.80 to 1.25, bioequivalence can still be concluded if the following criteria are met: 1) the point estimate of the adjusted GMR (Test/Reference) for  $C_{max,ss}$  and  $AUC_{tau}$  are contained in the range of 0.90 to 1.11, and 2) in vitro dissolution rates of Test (dry syrup) and Reference (tablet) formulations are available and are deemed similar according to [the Japanese bioequivalence guideline](#) (PSEHB/PED Notification No. 0319-1, 2020).

### 2.1 Multiplicity adjustment

Since the analyses of primary endpoints are planned at the interim analysis and the final analysis, Lan-DeMets alpha spending function approximating a Pocock boundary will be applied in order to control the overall Type I error rate.

## 3 POPULATIONS FOR ANALYSIS

### 3.1 Enrolled Set

All participants who have signed the informed consent will be included in the Enrolled Set (ES).

### 3.2 Randomized Set

All enrolled participants who were randomized will be included in the Randomized Set (RS).

### 3.3 Safety Set

All randomized participants who received at least 1 dose of the IMP will be included in the Safety Set (SS).

### 3.4 Pharmacokinetic Set

The Pharmacokinetic Set (PKS) consists of all study participants who are randomized, receive at least 1 dose of active IMP and have at least 1 quantifiable post-Baseline PK measurement.

All PKS participants who have a sufficient number of bioanalytical assessments to calculate reliable estimates for the primary PK parameters for both BRV formulations will be included in the statistical analysis.

If a participant's predose concentration on Day 1 is greater than 5% of the  $C_{max,ss}$  value on Day 3 in a Dosing Period, the participant's data from that Dosing Period will be excluded from the statistical analysis. If a participant's predose concentration on Day 1 is greater than 5% of the  $C_{max,ss}$  value on Day 3 for both Dosing Periods, the participant will be excluded from the statistical analysis.

If vomiting occurs at or before 2 times the median  $t_{max,ss}$  for the tablet and the dry syrup within a Dosing Period, the participant's data from that period will be excluded from the statistical analysis. If vomiting occurs at or before 2 times the median  $t_{max,ss}$  within a Dosing Period, for both Dosing Periods, the participant will be excluded from the statistical analysis.

If (1) a PK sample is missing and the  $C_{max,ss}$  is the sample immediately preceding or following the missing sample or (2) 2 or more samples are missing, then the participant's data from that period will be excluded from the statistical analysis.

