7.3 Lost to follow up

A participant will be considered lost to follow up if he fails to return for Dosing Period 2 or the SFU Visit and is unable to be contacted by the study site.

The following actions must be taken if a participant fails to return to the clinic for Dosing Period 2 or the SFU Visit.

- The site must attempt to contact the participant and reschedule the missed visit as soon as possible and counsel the participant on the importance of maintaining the assigned visit schedule and ascertain whether or not the participant wishes to and/or should continue in the study.
- Before a participant is deemed lost to follow up, the Investigator or designee must make every effort to regain contact with the participant (at least 1 phone call and 1 written message to the participant) and document his/her effort (date and summary of the phone call and copy of the written message in the source documents) to complete the final evaluation. All results of these evaluations and observations, together with a narrative description of the reason(s) for removing the participant, must be recorded in the source documents. The eCRF must document the primary reason for withdrawal.

Should the participant continue to be unreachable, he will be considered to have withdrawn from the study with a primary reason of lost to follow up documented in the eCRF.

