9.3 Planned outcome analyses

9.3.1 Pharmacokinetic analyses

Statistical analyses will be performed on the PKS.

All PKS participants who have a sufficient number of bioanalytical assessments to calculate reliable estimates for the primary PK parameters for both BRV formulations will be included in the statistical analysis.

If a participant's predose concentration is greater than 5% of the corresponding $C_{max,ss}$ value in a Dosing Period, the participant's data from that Dosing Period will be excluded from the statistical analysis. If a participant's predose concentration is greater than 5% of the corresponding $C_{max,ss}$ value for both Dosing Periods, the participant will be excluded from the statistical analysis.

If vomiting occurs at or before 2 times the median t_{max} for the tablet and the dry syrup within a Dosing Period, the participant's data from that period will be excluded from the statistical analysis. If vomiting occurs at or before 2 times the median $t_{max,ss}$ within a Dosing Period, for both Dosing Periods, the participant will be excluded from the statistical analysis.

Descriptive statistics will be used to describe all PK parameters for each BRV formulation. Listing of sampling time deviations, individual concentration-time data, and individual PK parameters will be generated. Graphical displays of individual and mean concentrations by time will also be presented on semilogarithmic and linear scales.

The bioavailability of BRV dry syrup (1.25g of granules for oral suspension 4% w/w, corresponding to 50mg of BRV) (Test) will be compared with BRV 50mg tablet (Reference).

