The primary PK parameters $C_{max,ss}$ and AUC_{tau} will be evaluated according to a linear mixed model, adapted to cross-over experimental designs. The model will include treatment (BRV formulation), period, and sequence as fixed effects. The participant (nested within the sequence) will be included as a random effect. Since the participant is entered as a random effect in the linear mixed model, the data from the nonaffected Dosing Period (ie, evaluable data) can still be used for the bioequivalence assessment even if the data from the other Dosing Period are excluded from the analysis. The dependent variables will be logarithmically (ln) transformed prior to statistical testing, following the usual recommendations. The CIs of the adjusted geometric mean ratio (GMR) (Test/Reference) will be calculated corresponding to the Lan-DeMets alpha spending function approximating a Pocock boundary (Lan and DeMets, 1983), while maintaining the overall 2-sided significance level of 0.1.

Bioequivalence between the Test (dry syrup) and Reference (tablet) formulations will be concluded if the CIs for $C_{max,ss}$ and AUC_{tau} are contained in the range of 0.80 to 1.25.

In the case that the CIs for $C_{max,ss}$ and AUC_{tau} are not contained in the range of 0.80 to 1.25, bioequivalence can still be concluded if the following criteria are met: 1) the point estimate of the adjusted GMR (Test/Reference) for $C_{max,ss}$ and AUC_{tau} are contained in the range of 0.90 to 1.11, and 2) in vitro dissolution rates of Test (dry syrup) and Reference (tablet) formulations are available and are deemed similar according to the Japanese bioequivalence guideline (PSEHB/PED Notification No. 0319-1, 2020).

The MIXED procedure in SAS software will be used for this analysis.

For $t_{max,ss}$, a distribution-free 90% CI (Hodges-Lehmann's method) will be calculated for the median difference between the tablet and the dry syrup formulations.

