9.5 Handling of protocol deviations

All protocol deviations will be reviewed on an ongoing basis as part of the data cleaning and evaluation process. After all data have been verified/entered into the database, and prior to database lock, a Data Evaluation Meeting will be performed for each cohort. The purpose of this review meeting will be to examine all protocol deviations, define the PKS (Section 9.1), and to verify the quality of the data. If PK parameters are needed to define the PKS, it will be performed based on the analysis data set of the pharmacokinetic parameters. The data evaluation will also help in guiding decisions on how to manage data issues on a case-by-case basis (eg, missing values, dropouts, and protocol deviations).

Accepted deviations from theoretical time points will be described in the appropriate documents and included in the electronic Trial Master File. After the data review, resolution of all issues, and documentation of all decisions, the database will be locked.

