In order to ensure a total of up to approximately 90 evaluable participants for the primary endpoints, assuming a rate of dropout and nonevaluable participants of approximately 5%, 64 participants for Cohort 1, 32 participants for Cohort 2, and up to 96 participants in total are estimated to be randomized in the study.

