#### **4.2.2 Main analytical approach**

The primary PK parameters  $C_{max,ss}$  and  $AUC_{tau}$  will be evaluated according to a linear mixed model, adapted to cross-over experimental designs. The model will include treatment (BRV formulation), period, and sequence as fixed effects. The participant (nested within the sequence)

will be included as a random effect. Since the participant is entered as a random effect in the linear mixed model, the data from the nonaffected Dosing Period (i.e., evaluable data) can still be used for the bioequivalence assessment even if the data from the other Dosing Period are excluded from the analysis. The dependent variables will be logarithmically (ln) transformed prior to statistical testing, following the usual recommendations.

This linear mixed model is represented as:

$$\log(Yijkl) = \mu + Si(j) + Qj + Fk + Pl + eijkl, \text{ where}$$

- $\log(Yijkl)$  is the log transformed PK parameter value of the  $i$ -th subject ( $i=1,2,3,..$ ) in the  $j$ -th sequence ( $j=1,2$ ); for the  $k$ -th treatment ( $k=1,2$ ) in the  $l$ -th period ( $l=1,2$ ),
- $\mu$  is the overall mean,
- $Si(j)$  is the random effect of the  $i$ -th subjects nested to the  $j$ -th sequence,
- $Qj$  is the fixed effect for the  $j$ -th sequence,
- $Fk$  is the fixed effect for the  $k$ -th treatment,
- $Pl$  is the fixed effect for the  $l$ -th period,
- $eijkl$  is the (residual) random error in observing  $\log(Yijkl)$ .

The MIXED procedure in SAS software will be used for this analysis.

For estimation based on a linear mixed model, covariance matrix applied to the within-subject error will be estimated by restricted maximum likelihood (REML). The Kenward-Roger approximation will be used to estimate the degree of freedom. Variance component structure will be used as covariance in this linear mixed model.

Adjusted geometric mean ratio (GMR) (Test/Reference) and the corresponding CIs will be calculated corresponding to the Lan-DeMets alpha spending function approximating a Pocock boundary ([Lan and DeMets, 1983](#)), while maintaining the overall 2-sided significance level of 0.1. Bioequivalence between the Test (dry syrup) and Reference (tablet) formulations will be concluded if the CIs for  $C_{max,ss}$  and  $AUC_{tau}$  are included in the range of 0.80 to 1.25. [IA-DMC, All]

SAS code for Lan-DeMets alpha spending function approximating a Pocock boundary

```
PROC SEQDESIGN bscale=pvalue;

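### Does the inclusion sentence that refers to both formulations conflict with keeping single-period data in the primary model?

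*SAP*

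**What the plan says.** Two kinds of statement sit close together in both documents.

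- **Inclusion.** Protocol 9.3.1 covers participants with enough data for "reliable estimates for the primary PK parameters for both BRV formulations will be included in the statistical analysis". SAP 3.4 repeats this for those with enough assay results "to calculate reliable estimates for the primary PK parameters for both BRV formulations will be included in the statistical analysis".
- **Exclusion by period.** If the predose concentration is above 5% of the maximum, or if there is early vomiting, then "the participant's data from that Dosing Period will be excluded from the statistical analysis" (the predose rule; the vomiting rule is parallel). The participant is removed only when both periods are affected. SAP 3.4 adds a period-level exclusion when two or more samples are missing, or when one missing sample adjoins the maximum.
- **Model.** Because participant is a random effect, SAP 4.2.2 says that "the data from the nonaffected Dosing Period (i.e., evaluable data) can still be used for the bioequivalence assessment" when the other period is excluded. Protocol 9.3.1 says the same: "the data from the nonaffected Dosing Period (ie, evaluable data) can still be used for the bioequivalence assessment".

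Loss between periods is foreseen. Protocol 7.3 treats a participant as lost to follow-up "if he fails to return for Dosing Period 2 or the SFU Visit" and cannot be contacted. Protocol 9.5 gives the Data Evaluation Meeting a part in "guiding decisions on how to manage data issues on a case-by-case basis (eg, missing values, dropouts, and protocol deviations"). Protocol 9.6 leaves missing data to the SAP. The sample size in Protocol 9.8 is set "assuming a rate of dropout and nonevaluable participants of approximately 5"%.

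**The concern.** A participant with one excluded period lacks reliable parameters for both formulations. He therefore seems to fail the inclusion sentence, while the exclusion rules and the model text keep him. Neither document states which takes precedence. A participant who leaves after Dosing Period 1 is in the Pharmacokinetic Set (one dose and one quantifiable measurement suffice), but no exclusion sentence mentions him.

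Two statisticians could therefore build different datasets for the confirmatory analysis of an open-label study. If the inclusion sentence were applied as a requirement, it would discard data that the mixed model was chosen to use. If the choice were left until the PK parameters were known, it could in principle be made with the result in view.

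**Working it through.** **1. The text.**

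- The inclusion sentence says that a group will be included. It does not limit inclusion to that group, so by itself it excludes nobody.
- The exclusion rules come in pairs: one affected period removes that period, and two remove the participant. If both formulations were required, one affected period would already remove the participant, and the second half of each pair would be redundant.
- The model sentence gives both the permission to keep the unaffected period and the statistical reason for it.
- A Dosing Period 2 that never took place has every sample missing. The SAP 3.4 rule on two or more missing samples removes that period, and SAP 4.2.2 leaves Dosing Period 1 usable. SAP 4.1 rules out imputation, so nothing else is available to put in its place.

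**2. The plan's own figures.** Inputs from Protocol 9.8: GMR 0.89, within-participant SD 0.183, limits 0.80 to 1.25, 60 then 90 evaluable participants.

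- Pocock-type spending at 60/90: 0.05 × ln(1 + 1.71828 × 0.6667) = 0.03817. The matching final level is 0.02704. Both agree with the plan.
- Standard error of ln GMR: 0.183 × √(2/60) = 0.0334.
- Power of the two one-sided tests with 58 degrees of freedom at 0.03817: 91.5% (plan: 90%, and about 91% for stopping).
- Randomized numbers: 60/0.95 = 63.2, so 64; 30/0.95 = 31.6, so 32; total 96, as planned.

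**3. How many participants are at issue.** The 5% covers dropouts and all other nonevaluable participants. At the planned rate, 64 − 60 = 4 is therefore the ceiling for single-period participants in Cohort 1.

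**4. Difference between the readings.** SAP 4.2.2 bases the information fraction on the Pharmacokinetic Set count, which includes Period 1-only participants under either reading. The interim level is thus the same for both: with 64 in the set, 0.05 × ln(1 + 1.71828 × 64/90) = 0.03992; with 62, 0.03905.

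The comparison simulates 400,000 trials per scenario. Each has 60 complete pairs, 30 per sequence, analysed with or without the Period 1-only participants, who are balanced by sequence. Estimation is by generalized least squares with participant random and the variance ratio known. The documents give no between-participant SD, so 0.15 to 0.30 is assumed. The EP0110 scenario uses GMR 0.87 and CV 21.9%, that is SD √ln(1 + 0.219²) = 0.2164 and standard error 0.0395.

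| Scenario | Period 1-only participants | Interim power, pairs only | Gain from adding them | Interim verdict differs |
|---|---|---|---|---|
| Design | 4 | about 91.9% | 0.2–0.5 points | 1.1–1.6% of trials |
| Design | 2 | about 91.7% | 0.1–0.2 points | 0.8–1.2% |
| EP0110 | 4 | about 63.4% | 0.4–0.9 points | 3.1–4.3% |
| EP0110 | 2 | about 63.1% | 0.2–0.4 points | 2.2–3.2% |

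In the design scenario with 4 such participants, the two estimates of ln GMR differ with an SD of 0.003 to 0.005, or 0.09 to 0.14 standard errors. The changes in verdict go both ways: about 0.6–1.0% of trials pass only with the extra data, and 0.4–0.6% pass only without it. These are interim rates. Unless futility is met, a trial that misses bioequivalence at the interim goes on to Cohort 2.

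**The case for a change.** The best case for a change is that the gap is narrowed but not closed. If the inclusion sentence is only a sufficient condition, no sentence states that single-period participants will be included. The model text says that their data can be used, which permits but does not require it, and it speaks of excluded data, not of a period that never happened. The word evaluable is also used two ways: the sample-size section counts a dropout as lost, while the model text calls one period's data evaluable. The Data Evaluation Meeting may use PK parameters in defining the analysis set, SAP 4.2.3 plans no sensitivity analysis, and a remedy would cost a few words.

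Part of this stands. No sentence names the participant who never starts Dosing Period 2, and no table is planned to count participants contributing one period and two.

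The suggestion of open discretion is weaker. The 5% predose rule needs the maximum concentration and the vomiting rule needs the median time to maximum, so the mention of PK parameters fits the listed exclusions. The meeting precedes database lock, the interim analysis belongs to a team independent of the study team, and exclusions from the analysis sets are listed with reasons. A low cost of rewording does not by itself make rewording necessary.

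**Conclusion.** No change is needed. The inclusion sentence is loosely worded, but read with its neighbours it has one sensible meaning: every evaluable period enters the mixed model, including Dosing Period 1 of a participant who does not return. An analyst following SAP 3.4 and 4.2.2 would get there without a further rule.

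Either reading gives a valid analysis if loss of a period is unrelated to the formulation difference. The gain from settling the wording is below 1 percentage point of interim power in every scenario examined, even when every planned loss in Cohort 1 is of this one type. That size rests on the planned 5% loss rate and on the assumed between-participant SD of 0.15 to 0.30. Losses well above plan would widen the difference between the readings, but would not change how the text is best read. A sentence in SAP 3.4 confirming this reading is optional; neither a protocol change nor a sensitivity analysis is called for.
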